Evaluation of ON/OFF (Investigator and self-assessment)		X		X					X	X	X	X	X	X				
Rescue OFF Tx allowed													X					
Usual morning anti-PD medication													X					
MDS-UPDRS Full ^h	X	X ^h		X											X			
MDS-UPDRS (III) motor (Cohorts 1 through 3)		X ⁱ						X ^j	X ^j	X ^j	X ^j	X ^j	X ^j					
MDS-UPDRS (III) motor (Cohort 4)		X ⁱ						X ^j		X ^j	X ^j	X ^j						
Prior and Concomitant Medications	X			X		CONTINUOUS												
Subject Questionnaire ^k													X					
Light Breakfast Offered		X		X														

Visit	1	2	3											4	
Day	Up to -21	Up to -20 to -1	-1	0											7
Window	N/A	N/A	N/A				See Footnotes (and Section 7.4.3)							± 10 mins	± 2 days ^a
Time (min)				Pre-dose	0	5	10	15	30	45	60	90	120	240	
Visit	Screening	Dopamine response	Treatment											Follow-up	
PK Blood Collection ¹ (Cohorts 1 through 3)				X					X		X	X	X		
PK Blood Collection ¹ (Cohort 4) Collected 1 minute prior to timepoint				X		X	X	X	X	X	X	X	X		

^a A +4 day window may be permitted in exceptional circumstances.

^b Prior to V2 and/or V3, subjects may attend the unit the previous evening and be domiciled overnight to allow early morning confirmation of their OFF state and facilitate scheduling of pre and post dosing procedures. Subjects not attending the unit the previous evening will arrive on Day 0.

^c Randomization may be performed on the day of dosing (Day 0) or the evening before (Day -1) for subjects being housed overnight prior to dosing.

^d Subjects should be rested in a recumbent position for ≥ 3 minutes prior to recording of ECGs. Subjects should be supine for at least 3 minutes prior to determination of supine vital signs (including blood pressure), after which they should stand and have only standing blood pressure measured immediately. Staff should be on hand to support subjects if required. ECGs and vital signs should be assessed after UPDRS assessment and PK blood draws. Sites may follow their usual sequence of procedures for recording vital signs and ECG where they occur together. The window allotted for vital signs will be +15 minutes at the 30 and 60 minute post-dose timepoints. The vital signs and ECG collection at 120 minutes may occur up to 180 minutes. Due to variability in assessment length, assessments collected out of window, with the exception of PK samples and UPDRS, will not be considered deviations.

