^e Complete physical examinations (including nasal examination) should be conducted at Screening, Day 0 (pre-dose only) and end of study visits. A directed physical examination will be conducted at 120 minutes post-dose at Visit 3 only and may occur up to 180 minutes.

^f 60 ±5 minutes pre-INP103 or placebo administration in Cohorts 1, 2 and 3 only.

^g Subjects will be randomized to INP103 (35, 70 or 140 mg; n=6 to each dose) or placebo (n=2) in each of Cohorts 1, 2 and 3 and to INP103 with carbidopa (70 mg L-dopa/7.0 mg carbidopa; n=6) or placebo (n=2) in Cohorts 4. At the discretion of the Sponsor, depending on rate of recruitment, cohort 4 may be over enrolled with a total of up to 12 subjects using the 3:1 randomization scheme. In Cohort 4, dosing may commence as soon as OFF state has been confirmed and all baseline assessments have been completed and will not include oral benserazide.

-
- ^h Full MDS-UPDRS (Parts I-IV) will be assessed on arrival at clinic for dopaminergic responsiveness assessment at Visit 2 during Screening. Subjects will omit their usual anti PD therapy from 22:00 the previous evening and should arrive at the clinic in an OFF state.
- ⁱ Once a full MDS-UPDRS assessment has been undertaken, subjects will take their usual 'ON' medication and repeat only the MDS-UPDRS Part III (motor) assessment at +15, +30, +45, +60, +90 and +120 minutes for C1, C2, C3, and +30, +60, +90, and +120 for C4. Subjects demonstrating a 30% improvement in MDS-UPDRS Part III (motor assessment) within the 120 min will be deemed dopamine responsive and will be eligible for randomization.
- ^j MDS-UPDRS Part III is assessed after PK blood draws and actual time will be recorded (time from dosing to START of assessment).
- ^k Subject Questionnaire may be administered from 120 minutes up to 180 minutes to allow other study assessments to occur first.

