- ^l Baseline PK samples will be taken within 15 minutes prior to dosing. For Cohorts 1-3; the time window for blood sample collection is ± 5 minutes for the samples through 120 minutes. Actual time samples taken will be used for PK analysis. PK blood draws will occur AS SOON AFTER MDS-UPDRS Part III assessments as possible (even if outside of the ± 5 minute window) and time noted. **FOR COHORT 4 ONLY:** PK sample collection will occur 1 minute prior to the timepoint (samples will be collected at 4, 9, 14, 29, 44, 59, 89, and 119 minutes post-dose). For Cohort 4; the window for blood sample collection is up to +1 minute for timepoints 5 minutes up through 30 minutes and ± 2 minutes for timepoints 45 minutes through 120. PK blood draws will occur IMMEDIATELY PRIOR TO MDS-UPDRS Part III assessments as possible (even if outside of the time window) and time noted.
- ^m Only required if no documented history of an MMSE within 36 months prior to Screening.
- ⁿ A light breakfast should be offered to the patient 30 minutes prior to dosing; see [section 4.7](#).

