6. STUDY PROCEDURES

Study visits should be completed as indicated in the Study Schedule located in [Table 1](#).

Blood samples for L-dopa PK should be collected at the time points and within the windows designated in [Table 1](#)

Sites should prioritise in the following order: PK blood draws; UPDRS/Dyskinesia assessments; other safety assessments. All procedures should be completed as close to the prescribed/scheduled times as possible and may be conducted in sequence by the sites according to their standard practice. Due to variability in assessment length, assessments collected out of window, with the exception of PK samples and UPDRS, will not be considered deviations. Any non-scheduled procedures required for urgent evaluation of safety concerns take precedence over all scheduled routine procedures.

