6.5. Pharmacokinetic Assessments

6.5.1. Sampling and Processing

An intravenous cannula will be inserted prior to all medication dosing at Visit 3 to enable baseline PK and subsequent blood draws to be performed.

Blood samples for PK analysis of L-dopa (and carbidopa in Cohort 4) will be obtained, according to the site's SOPs, within 15 minutes prior to INP103 or placebo dosing and at the time-points (related to INP103/placebo dosing), and within the windows, delineated in the Study Schedule in [Table 1](#).

The actual collection time of each sample must be recorded in the source data documentation, on the collection tube and in the electronic case report form (eCRF). The allowed time deviation window for blood sample collection is + 1 minute for samples up to 30 minutes, and then \pm 2 minutes for the 44, 59, 89 and 119 minutes sample time points (following INP103/placebo dosing) before a deviation is recorded. PK blood draws will precede UPDRS assessments. Due to variability in

assessment length, assessments collected out of window, with the exception of PK samples and UPDRS, will not be considered deviations

The Sponsor will supply complete written instructions for handling, processing, storage, and shipping of PK samples in the laboratory manual prior to study initiation.

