7.4.3. After Dosing

The subjects will remain in the study clinic post-dose through to the completion of all scheduled post-dose procedures 240 minutes after dosing.

The subject's usual rescue (anti-OFF [e.g. Madopar rapid]) medication will be permitted from 120 minutes post-dose (once all 120 minute assessments have been completed, but can precede ECG, physical examination and subject questionnaire) – if they are still OFF. In addition, subjects should take their regular anti PD medication (e.g. their regular morning Madopar dose) at 120 minutes post dosing whether or not they have returned to ON.

The following in-patient assessments will be performed after dosing:

1. Adverse Events (including overall dyskinesia rating) and concomitant medications will be continually monitored post-dose.
2. Vital signs will be measured at 30, 60 and 120 minutes post-dose. Blood pressure (supine and standing) and heart rate, respiratory rate and oral temperature (supine only) will be measured at all time points. Vital signs will be collected after MDS-UPDRS assessment (where both procedures are scheduled at the same time point) and will not be deemed protocol deviations if they occur outside the time window at each timepoint.
3. PK blood samples will be collected at 4, 9, 14, 29, (all + 1 minute) 44, 59, 89 and 119 (all \pm 2 minutes at each timepoint) minutes post-dose and will precede UPDRS assessments.
4. MDS-UPDRS III only at 15, 30, 45, 60, 90 and 120 minutes post-dose for Cohorts 1, 2 and 3) and 30, 60, 90, 120 minutes for Cohort 4 (\pm 2 minutes at each timepoint)
5. Investigator and subject self-assessment of ON/OFF at 30, 45, 60, 90, 120 and 240 minutes post-dose (\pm 10 minutes at each timepoint)
6. At 120 minutes, the subject's usual morning dose of all Parkinson's medications should be given following completion of assessments 1-5, regardless of ON/OFF state. In addition, if subject is still OFF, their usual OFF medication may be given (prior to completing assessments 7, 8 and 9).
7. Directed physical examination (including nasal inspection) will be performed at 120-180 minutes post-dose

8. 12-Lead ECG will be performed at 120-180 minutes post dose. In cases where vital signs are scheduled at the same time point, ECG will be completed in sequence with vital signs per the usual practice of the study sites.
9. Subject questionnaire will be completed as the last assessment from 120-180 minutes post-dose

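### For Cohorts 1–3, Table 1 footnotes j and l put the PK draw and the Part III exam in opposite orders at all four post-dose PK times

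*Protocol*

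**What the plan says.** Protocol Table 1 tags every post-dose Part III mark for Cohorts 1–3 with footnote j: "MDS-UPDRS Part III is assessed after PK blood draws and actual time will be recorded". The PK row for the same cohorts carries footnote l. Its first part sets a ±5 minute window for Cohorts 1–3 and then says "PK blood draws will occur AS SOON AFTER MDS-UPDRS Part III assessments as possible", even if that takes the sample outside ±5 minutes. Its second part, marked for Cohort 4 only, puts the draw immediately before the exam and also tolerates out-of-window draws.

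Three other places touch the order:

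- Protocol Section 6 ranks PK draws above the UPDRS, but adds that procedures "may be conducted in sequence by the sites according to their standard practice".
- Protocol Section 6.5.1 says "PK blood draws will precede UPDRS assessments". The times and windows beside it (44, 59, 89 and 119 minutes; +1 and ±2 minutes) are those of Cohort 4, with no cohort named.
- Protocol Section 7.4.3 item 3 also puts the draw first, and again lists Cohort 4 times without a label: "PK blood samples will be collected at 4, 9, 14, 29" and onwards. Item 4 gives "MDS-UPDRS III only at 15, 30, 45, 60, 90 and 120 minutes post-dose for Cohorts 1, 2 and 3", with a ±2 minute window.

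**The concern.** Staff who read the exam row would draw blood and then examine. Staff who read the PK row would examine and then draw. SAP 8.1 expects five sites, so the order could differ between sites, and it could differ between Cohorts 1–3 and Cohort 4.

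The PK/PD relationship is a secondary objective, and the display specified for it (SAP 13.3, Figure 14.2.3.1) plots change in Part III against time-matched L-dopa concentration. SAP 13.3 does not say whether matching uses nominal or recorded times. With mixed order, some points would pair a score with a concentration taken before the exam and others with one taken after it. The 30-minute point is also the primary motor function endpoint.

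SAP 13.1.1 summarises concentrations and draws mean profiles at nominal times. Cohorts 2 and 4 share the 70 mg L-dopa dose, so they could be shown at the same time point although sampled on opposite sides of the exam. SAP 13.1.2 uses nominal times for interim PK parameters, so a delayed draw would make interim Tmax look earlier than it was.

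**Working it through.** No power or alpha figure is involved. The check sets the texts side by side and adds simple timing arithmetic.

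**1. Shared times (Table 1).** The Cohort 1–3 post-dose PK marks are at 30, 60, 90 and 120 minutes. The Part III marks are at 15, 30, 45, 60, 90 and 120 minutes. The overlap is 30, 60, 90 and 120, so all 4 of the 4 post-dose PK times are affected. The PK times rest on the Table 1 columns alone, because Sections 6.5.1 and 7.4.3 list the Cohort 4 schedule.

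**2. Order given for Cohorts 1–3.**

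| Place | Order | Clearly about Cohorts 1–3? |
|---|---|---|
| Footnote j | draw, then exam | Yes: tagged on their exam marks |
| Footnote l, first part | exam, then draw | Yes: cites their ±5 minute window and precedes the Cohort 4 part |
| Section 6 | PK has priority; sequence left to the site | General |
| 6.5.1 and 7.4.3 item 3 | draw, then exam | Unclear: Cohort 4 times and windows, no label |

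The general text leans towards drawing first. It does not clearly override footnote l, which is the most specific instruction for these cohorts.

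**3. Samples affected.**

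- All three cohorts under this wording: 3 × 8 × 4 = 96, of which 3 × 6 × 4 = 72 are on INP103.
- Only Cohort 3: 8 × 4 = 32, of which 6 × 4 = 24 are on INP103.

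The range is needed because SAP 5.1 cites protocol v3.0 for the interim on Cohorts 1 and 2, while the SAP itself is based on Amendment 4. The documents do not show which wording governed the earlier cohorts.

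**4. Timing gap against Cohort 4.** Let L be the exam length in minutes, which the documents do not give. Assume the exam starts on time, the blood is drawn the moment the exam ends, and Cohort 4 is sampled at its scheduled minute.

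- At 30 minutes: (30 + L) − 29 = L + 1.
- At 60 minutes: (60 + L) − 59 = L + 1, and likewise at 90 and 120.

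For scale, L = 5 gives 6 minutes. Exams starting exactly 15 minutes apart leave room for L of at most 15, which gives 16 minutes. These figures are conditional on the assumptions above. Real gaps may be larger or smaller, because footnote l lets both groups draw out of window.

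**5. Footnote l against its own window.** If the exam starts s minutes from nominal, a draw at its end is within +5 only if s + L ≤ 5. For s = −2, 0 and +2 this requires L ≤ 7, 5 and 3 minutes.

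**6. Where draw time enters the analysis.** Final PK parameters and individual concentration profiles use actual times. Concentration summaries, mean plots and interim PK parameters use nominal times. The basis for the PK/PD plot is not stated.

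**The case against.** The strongest reply is that the protocol has already decided. Section 6.5.1 states draw-first without restriction, 7.4.3 agrees, and Section 6 ranks PK first. Actual draw times and exam-start times are recorded, final PK parameters use actual times, the SAP has no formal PK or PD hypotheses, and the interim is for information only. Cohorts 2 and 4 already differ in decarboxylase inhibitor, sampling grid and windows, and no test between them is planned.

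Most of this stands and limits the consequence. It does not remove the conflict, because the unrestricted sentence sits among Cohort 4 times while footnote l speaks directly to Cohorts 1–3.

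A reader might infer more than the documents support:

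- *That drawing first fits every window whatever the exam length.* It does not. The exams at 15, 30, 45 and 60 minutes must start between 13 and 62 minutes. With draws of d minutes before the 30- and 60-minute exams, 3L + 2d ≤ 62 − 13 = 49. Even with d = 0, L cannot exceed 49/3, about 16.3 minutes.
- *That footnote l contradicts the deviation rule.* Section 6 says "assessments collected out of window, with the exception of PK samples and UPDRS, will not be considered deviations", so late PK samples are not exempt. But a late draw can be allowed, timed and still logged as a deviation.
- *That PK results are biased by a known amount.* Neither L nor human Tmax is given. Protocol 1.2.1 reports Tmax in monkeys only.
- *That sites did differ in order.* The documents show only that they could.

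**Conclusion.** The contradiction is real: for Cohorts 1–3, footnotes j and l cannot both be followed at 30, 60, 90 or 120 minutes, and nothing else in the protocol clearly decides between them. It is a minor point, although the order changes what sites do and what the PK/PD plot pairs.

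Between 32 and 96 planned samples are affected (24 to 72 on INP103), depending on which cohorts were sampled under this wording. The shift relative to Cohort 4 is about L + 1 minutes under the on-schedule assumptions above, with L unknown. The consequence is limited to the exploratory PK/PD plot, the nominal-time concentration summaries and mean plots, and the interim PK. The documents do not support extending it to the final PK parameters.

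**What to change.** - **Footnotes j and l:** state one order for Cohorts 1–3. For samples not yet drawn, take blood immediately before Part III. This matches footnote j, Sections 6.5.1 and 7.4.3, and Cohort 4.
- **Sections 6.5.1 and 7.4.3 item 3:** label the listed times and windows as Cohort 4 only.
- **If earlier cohorts were drawn after the exam:** report the order used in each cohort. Pair PK and Part III in the SAP 13.3 plot using recorded draw and exam-start times. Give the range of actual draw times under each nominal-time summary.

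The cost is a wording amendment to the footnotes, labels in two sections, and notes built from times already being recorded. There are two downsides. Samples already drawn cannot be corrected, only described. A mid-study switch may also create a difference in order between dose levels, which would have to be reported.

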1. BACKGROUND AND INTRODUCTION

1.1. Introduction

The purpose of this study is to evaluate the INP103 drug-device combination product specifically as it pertains to the intranasal administration of L-dopa (levodopa; L-3,4-dihydroxyphenylalanine) to the upper nasal cavity using the I231 Precision Olfactory Delivery (POD) device. L-dopa is the immediate metabolic precursor to the neurotransmitter dopamine; following crossing of the blood brain barrier, in a healthy brain, exogenous L-dopa is rapidly converted to dopamine. Dopamine itself cannot cross the blood brain barrier. Levodopa is given in combination with a decarboxylase inhibitor (DCI), which is either benserazide (in the brand Madopar®) or carbidopa (in Sinemet®) to ensure the L-dopa is not metabolized in the periphery before it can cross into the brain. INP103 is an experimental nasal L-dopa product. In Cohorts 1, 2, and 3 of this study, the DCI benserazide will be delivered orally 60 minutes before intranasal dosing with INP103. In Cohort 4, the INP103 formulation will contain the DCI, carbidopa, in a w:w ratio of 10:1 (L-dopa:carbidopa, the lowest ratio for oral co-administration) and will not require pre-treatment with an oral DCI. Neither DCI has any pharmacological activity other than to inhibit dopa decarboxylase. Cohort 4 will receive the same dose of L-dopa as in Cohort 2 and lower DCI levels than the orally administered benserazide.

PD is a degenerative disorder of the central nervous system characterised by involuntary muscle movements (dyskinesias, including tremors), rigidity, slowness of movement and potential cognitive impairment. Motor symptoms are linked with depleted dopamine in the basal ganglia. As such, the first line of therapy in the management of PD is administration of L-dopa, which was first investigated in 1961 (1).

Use of L-dopa is long established, but a number of limitations persist, namely:

- Penetration of L-dopa into the brain is limited by the presence of L-dopa decarboxylase and monoamine oxidase within the capillary endothelial cells. Together these form an enzymatic blood-brain barrier that limits passage of L-dopa into the brain.
- Systemic L-dopa that does not pass the blood brain barrier causes side effects in the peripheral nervous system requiring co-administration of a L-amino acid decarboxylase inhibitor (DCI; typically, benserazide or carbidopa in combination with L-dopa).
- Lastly, a progressive decline in L-dopa responsiveness occurs that leads to switches between mobility and immobility (ON and OFF periods, respectively) in L-dopa-treated patients. These ON/OFF oscillations have

been reported in at least 50% of PD patients who have been receiving L-dopa for 5–10 years and constitute a major cause of disability in advanced PD.

Impel's INP103 drug-device combination product is designed to deliver drugs (in this case L-dopa with or without DCI) to the upper nasal cavity. This region of the nasal cavity has many advantages for drug delivery. Administering drugs to the upper nasal cavity may reduce the overall variability and improve bioavailability by minimizing the amount of drug that drips out of the nose or runs into the posterior pharynx after nasal administration. In addition, the upper nasal cavity is highly vascularized for rapid drug absorption into the plasma. The upper nasal cavity is the only region of the body that has direct connections to the central nervous system via the olfactory and trigeminal nerve routes (2). Therefore, administration of central nervous system drugs to this region of the nasal cavity may lead to direct uptake into the brain. All of these factors make the upper nasal cavity a desirable route of administration for central nervous system-targeted drugs.

Impel has been developing both an INP103 levodopa-only formulation that would need to be administered in the presence of an oral DCI, and a variation of the INP103 formulation containing carbidopa to obviate the need for an oral DCI to be administered 60 minutes before dosing. Both DCIs to be used in this study are approved for use in Australia.

INP103 is anticipated to rapidly deliver L-dopa, the dopamine precursor, to the brain via the vasculature and potentially the direct nose-to-brain pathway, thereby permitting rapid and efficient resolution of OFF periods in subjects in receipt of oral L-dopa. The present study is a proof of concept investigation of the INP103 drug-device combination product incorporating the nasal delivery of L-dopa (with or without carbidopa) by the I231 POD Device.

1.2. Summary of Non-Clinical and Clinical Studies

1.2.1. Non-Clinical Studies

Oral L-dopa has been extensively used in the treatment of PD and is supported by a literature evidence base. A review of literature is provided in the Investigator's Brochure. In addition, Impel NeuroPharma has performed the following studies:

- Six studies in the cynomolgus monkey examined the PK of powder L-dopa formulations, including two studies testing L-dopa formulations containing carbidopa, using a non-human primate version of the clinical POD Device (nhpPOD). The dose of L-dopa per nasal surface area varied from approximately 0.5 to 1.2 mg/cm², similar to the local nasal concentrations estimated to be achieved clinically (0.4375–0.875 mg/cm²) following doses of 35–140 mg L-dopa to the nose. No clinical observations were noted.

- Study 1: Following intranasal administration of unmodified crystalline L-dopa (of particle size $D_{50} = 50 \mu\text{m}$) in the absence of benserazide, dose-dependent PK was shown (10-40 mg dose range). The C_{max} following 40 mg L-dopa administration was 150 ng/mL, and the T_{max} was delayed, showing an average of ≥ 75 minutes. A smaller particle size (20-40 μm) crystalline L-dopa material was also tested and indicated a higher exposure compared to an equivalent dose of an unmodified L-dopa formulation.
- Study 2: The PK of intranasal L-dopa in combination with oral benserazide was explored (4 x 5mg administered over 24hr predose), demonstrating similar PK across four L-dopa formulations containing crystalline particle size sifted L-dopa (20-40 μm), spray dried L-dopa only (particle size D_{50} 10-30 μm), spray dried L-dopa with sodium chloride (L-dopa:NaCl) and spray dried L-dopa with sodium chloride and HPMC (L-dopa:HPMC:NaCl). C_{max} concentrations of >900 ng/mL were achieved following a dose of 20 mg (10 mg/nostril) of each formulation, which is above the threshold necessary for efficacy of OFF episode treatment. C_{max} was approximately 10-fold higher in the presence of benserazide. Median T_{max} was 45 to 60 minutes, an improvement over the T_{max} observed in the absence of benserazide.
- Study 3: A third study in the monkey explored the PK of intranasal L-dopa in a further five spray dried formulations in combination with oral benserazide (see below). All formulations achieved similar or up to 1.7-fold greater total exposure (AUC) and up to 2.3-fold increased C_{max} compared to spray dried formulations tested in the second PK study. Median T_{max} (53–105 minutes) for Groups 1, 2, 3 and 5 was similar or greater than T_{max} in the second study. T_{max} for Group 4 was significantly faster (median 30 minutes, with all four monkeys achieving >400 ng/mL L-dopa within 7 minutes of dosing). Since the product is intended to achieve plasma concentrations of L-dopa (>400 ng/mL) sufficient to rapidly switch a patient from OFF to ON, the maltoside-containing formulation was selected for testing in the proposed clinical study.

Group 1: L-dopa:NaCl:HPMC:DSPC (68:2:16:14)

Group 2: L-dopa:NaCl:HPMC:DSPC (68:2:23:7)

Group 3: L-dopa:NaCl:HPMC:DSPC (68:2:23:7, minor manufacturing change compared to Group 2)

Group 4: L-dopa:NaCl:HPMC:Maltoside (68:2:23:7)

Groups 1 to 4 received pre-treatment with benserazide at -24, -16, -8 hours and -45 minutes

Group 5: L-dopa:NaCl:benserazide:HPMC:DSPC (68:2:7:16:7), pre-treated with benserazide at -24, -16 and -8 hours

- Study 4: A fourth study determined PK of intranasal L-dopa in five spray dried formulations with a reduced concentration of maltoside (1% w/w) in combination with oral benserazide. All formulations contained 68% L-dopa and 2% NaCl; three formulations included 29% w/w HPMC and 1% w/w maltoside (prepared by small modifications of the spray drying process) and two formulations contained 29.9% w/w HPMC with 0.1% w/w maltoside or 29.5% HPMC with 0.5% w/w maltoside. Each group (N=4) received four oral 5 mg benserazide pre-treatments at -24, -16, -8 and -0.75 hours before L-dopa formulation delivery by the nhpPOD Device. All formulations tested achieved similar AUC and C_{max} levels compared to the third monkey PK study. Compared to the formulation in the third monkey PK study containing 7% maltoside, median T_{max} was slightly delayed (<2.3-fold, range 37.5-68 minutes across all groups compared to 30 minutes). However, while T_{max} was slightly delayed, individual plasma levels following the Group 3 formulation (29% HPMC with 1% maltoside) increased rapidly and more consistently to achieve levels >400 ng/mL L-dopa within 15 minutes. This formulation was selected for GMP manufacture and for inclusion in the proposed clinical study.
- Study 5: A PK and safety study of the nasal administration of L-dopa powder formulation containing carbidopa (Study 2037-017, N=20), in the absence of an orally administered DCI, demonstrated plasma exposures similar to the above referenced monkey PK studies (2037-003, 2037-004, 2037-006, 2037-007) where formulations of levodopa were nasally administered after administration of an oral DCI (benserazide). Maximum plasma concentration (C_{max}) of 560 ng/mL - 1,608 ng/ml were achieved following 20 mg L-dopa administration with median T_{max} between 38-68 minutes. The group receiving a formula the same as the formula to be used in Cohorts 4-5 (BG54-126; levodopa: carbidopa: HPMC: maltoside:NaCl (68: 6.8: 22.2: 1: 2) resulted in an AUC of $149,941 \pm 22,112$ ng*min/ml, a C_{max} of $1,608 \pm 198$ pg/ml, and a T_{max} of 53 minutes. These values are similar to the levodopa alone formulation administered in the above reference monkey study 2037-007 in which a formula representative of that being used in Cohorts 1-3 of the clinical study resulted in an AUC of $92,404 \pm 18,094$ ng*min/ml, a C_{max} of $1,310 \pm 413$ pg/ml, and a T_{max} of 53 minutes.
- Study 6: A PK and safety study in monkey (Study 2037-019, N=20) was conducted to explore the PK of nasal administration of L-dopa with the DCI carbidopa present in the formulation, in a ratio of either 1:4, 1:10, or 1:20. The goal of this study was to evaluate the potential effect on

safety and plasma exposure of different ratios of carbidopa in the formulation. This study resulted in similar plasma exposures to the previous study (2037-017) with C_{\max} values between 899 – 1,167 ng*min/ml and T_{\max} between 45 – 60 minutes. There were no clinical signs of intolerance or safety signals observed in the study.

In all six studies, detailed clinical observations of each animal were performed pretest and at various intervals post dosing ranging from 15 minutes up to 120 minutes after dosing. The clinical observations included, but were not limited to, evaluation of the nose, oral cavity, skin, fur, eyes, ears, thorax, abdomen, external genitalia, limbs and feet, respiratory and circulatory effects, autonomic effects such as salivation, and nervous system effects. No observations were made indicating an issue with tolerability or irritation from the intranasal formulation to be used in the clinical trial.

